3.3 Sample size and power calculation

A PPS of hospital antimicrobial use in four general hospitals in Laos in 2017 showed 13% compliance to Lao treatment guidelines (LOMWRU unpublished data) but previous guidelines did not contain much information on antibiotic prescribing, therefore reliable baseline data are lacking.

The sample size of 6 hospitals was estimated assuming 30% of antimicrobial prescription adherence with the paper-based prescribing guideline (reference), and assuming 0.05 intra-cluster correlation coefficient. This will have 80% of power of the test to be able to detect 15% minimum difference after introduction of the mobile phone app prescribing guidelines at 0.05 significant level.

This will be a 3-step trial with one baseline measurement after introduction of the paper-based prescribing guidelines. The outcomes will be measured every four months. These will give four outcomes measurements in total (excluding baseline measurement at start), until the trial

completes at month 16.

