After the first paired hospital is randomly selected to have access to the mobile phone app prescribing guidelines at month 4, the second pair of hospitals will be randomly selected to have access to the mobile phone app at month 8, and the last pair of hospitals will have access to a mobile phone app at month 12 (Figure 2).

The order of activities at the start of the project are listed below (these activities will be applied to all six hospitals, one by one):

1. PPS on hospital antimicrobial use for all 6 hospitals (Appendix A1, A2 and A3)
2. AMS knowledge survey (Appendix A5)
3. Pre-prescribing guidelines survey (Appendix A9)
4. Access to paper prescribing guidelines for all 6 hospitals
5. Introductory session to paper prescribing guidelines (Appendix A6)
6. PPS reports (Appendix A4)

Activities in the reference phase after the start of the project (month 0) until the last paired hospital is assigned to the intervention (month 12) are listed below:

1. PPS on hospital antimicrobial use (Appendix A1, A2 and A3)
2. PPS reports (Appendix A4)

c. Intervention phase

c.1 Antimicrobial Prescribing guidelines mobile phone application (MicroGuide)

Both paediatric and adult antimicrobial prescribing guidelines will be transferred to [MicroGuide](#); which is a medical guideline application. MicroGuide was launched in 2013 and has been adopted by 114 medical organizations, with more than 100,000 users in 173 countries. MicroGuide is an offline application, free-of-charge for the individual users. The app can monitor the number of users and which guidelines are being accessed.

The app will be installed to the personal smart phones of local physicians by the PI. The project will not provide a smart phone to any physician without one (approximately <10% of physicians in provincial hospitals– unpublished data). The contents of the mobile app guidelines will be the same as the paper version but using hyperlinks to information, rather than displaying it as in paper guidelines. Both mobile app and paper guidelines will be available in Lao and English languages.

c.2 Antimicrobial stewardship (AMS) training

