measured cross-sectionally at month 0, 4, 8, 12 until month 16 after introduction of prescribing guidelines by mobile phone application versus paper-based (30). The model will compare all wedges in the intervention from month 4 to month 16 with all wedges in the reference arm from month 0 to month 12. The duration of exposure of each hospital to the reference or intervention arm will be included in the model as interaction term with the study arm in order to assess whether the duration of exposure is the effect modifier. The model will consider the correlation among the outcome's measurements from the same hospital (cluster) by adjusting for clustering in the model. Odds ratios and the corresponding confidence intervals will be obtained and reported. Tests of significance will be performed at 5% level. Analyses will be done using Stata 15.0 or higher. Likert scale analysis will be used to evaluate prescriber satisfaction with/ acceptability of paper-based compared to mobile phone app delivered antimicrobial prescribing guidelines. The satisfaction/acceptability scale will be assigned in six categories, including strongly agree=5, agree=4, neutral=3, disagree=2 and strongly disagree=1, no opinion/not use=0. Mann-Whitney test will be used to assess the differences between paper-based population and mobile phone app population. AMS knowledge level of prescribers will be assessed using questionnaires based on information in the prescribing guidelines. The overall proportion of correct answers in each time point will be compared (baseline, after paper-based guidelines (before AMS training and introduction of mobile phone app guidelines) and after AMS training and introduction of mobile phone app guidelines). Other factors such as extra AMR training program from hospital/MoH/other organizations, level of education and specialties of prescribers will also be taken into account.

Cost of antibiotic therapy will be calculated from the start date of treatment to the survey day. The unit costs for the antibiotics will be obtained from the [International Medical Product Price Guide](#).

Antibiotic defined daily dose (DDD) will be calculated using data (antibiotic agent, start date, dose and DDD of each antibiotic from www.whooc.no) from PPS in both IPD and OPD. Antimicrobial cost data from participating hospitals will also be collected each hospital pharmacy for comparison with international cost.

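### The only primary model contains an arm-by-exposure-duration interaction without saying how duration is coded or which odds ratio is primary, while the 80% power is for one overall app effect

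*Combined protocol and SAP*

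**What the plan says.** The Statistical analysis text (section 3.7, repeated in the Trial synopsis) describes one logistic mixed-effects model for adherence. It sets all app wedges against all reference wedges and allows for clustering by hospital. It then states that "The duration of exposure of each hospital to the reference or intervention arm will be included in the model as interaction term" with study arm, to learn whether duration modifies the effect. After that, "Odds ratios and the corresponding confidence intervals will be obtained and reported" and "Tests of significance will be performed at 5% level".

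The text does not say whether duration is continuous, centred or categorical, whether a model without the interaction is also fitted, or which contrast is primary. Survey-month effects are not mentioned.

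Section 3.3 gives the power basis: "The sample size of 6 hospitals was estimated assuming 30% of antimicrobial prescription adherence with the paper-based prescribing guideline (reference"), "assuming 0.05 intra-cluster correlation coefficient", and "This will have 80% of power of the test to be able to detect 15% minimum difference". That is one difference with no exposure duration attached. The primary endpoint in section 3.6 points elsewhere, to month 16 with twelve months of exposure in each group.

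Timing matters here. In the start-up list of section 3.5 b the survey comes first and "Access to paper prescribing guidelines for all 6 hospitals" comes fourth, so the month 0 survey precedes the paper guidelines. In section 3.5 c.3 and Appendix A7, each pair's crossover survey precedes the app.

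**The concern.** With an arm-by-duration interaction in the model, the arm coefficient is not an overall effect. It is the effect at whatever duration is coded as zero or as the reference level. The plan fixes neither, so the fit can yield an odds ratio at 0 months, at mean exposure or at 12 months. Their precision differs greatly, and their values may differ too. In an open-label trial that choice should not be left until the data are seen.

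Two features of the design sharpen this. At zero duration there is no app survey, and the only reference survey there was taken before any paper guideline was issued. Also, all hospitals start paper together, so paper duration is the same variable as calendar month. A paper-duration slope and survey-month effects therefore compete for the same information.

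**Working it through.** **Inputs from the documents.** 6 hospitals, 2 per step; 30% against 45% (the 15% read as percentage points); ICC 0.05; alpha 0.05, taken as two-sided. Section 3.3 states "This will be a 3-step trial with one baseline measurement after introduction of the paper-based prescribing guidelines" and four measurements besides the month 0 survey, so I ran months 4–16 and months 0–16.

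**Assumption.** Prescriptions per hospital-survey (m) are not stated. I solve for m and also show m = 100.

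**App exposure at surveys.** The pairs cross at months 4, 8 and 12, after that month's survey. App hospital-surveys fall at 4 months (6), 8 months (4) and 12 months (2), a mean of (6×4 + 4×8 + 2×12)/12 = 6.67. None falls at 0.

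**Reproducing the 80%.** Total variance is 0.375 × 0.625 = 0.2344. Between-hospital variance τ² = 0.05 × 0.2344 = 0.01172. Within-hospital variance of a survey mean is σ² = 0.95 × 0.2344/m. The Hussey–Hughes variance, with survey-month effects and a common app effect, is

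Var = Iσ²(σ² + Tτ²) / [(IU − W)σ² + (U² + ITU − TW − IV)τ²].

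For months 4–16: I = 6, T = 4, U = 12, W = 0 + 4 + 16 + 36 = 56, V = 2(9 + 4 + 1) = 28. With m = 44, σ² = 0.00506, so Var = 0.001577/(16 × 0.00506 + 40 × 0.01172) = 0.001577/0.5497 = 0.00287 and SE = 5.4 points. Power = Φ(15/5.36 − 1.96) = 80%. For months 0–16 the required m is about 40. The 80% is attainable for a common effect, but not reproducible without m.

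**Adding duration.** On the same hospital-survey means, Var(c′b) = c′(X′V⁻¹X)⁻¹c. X holds arm, duration in either arm and their product. The contrast is arm + e × interaction, with both arms at duration e. The true effect is a constant 15 points.

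Model as written (no survey-month effects), SE in points and power:

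| Surveys | m | Common effect, no duration terms | e = 0 | e = 6.67 | e = 12 |
|---|---|---|---|---|---|
| 4–16 | 44 | 3.2; >99% | 7.4; 53% | 3.2; 99.7% | 7.3; 54% |
| 0–16 | 44 | 2.8; >99% | 5.7; 74% | 3.1; 99.8% | 6.4; 65% |
| 4–16 | 100 | 2.1; >99% | 4.9; 86% | 2.1; >99% | 4.9; 87% |
| 0–16 | 100 | 1.9; >99% | 3.8; 98% | 2.1; >99% | 4.3; 94% |

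With survey-month effects added:

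| Surveys | m | Common effect | App duration only, e = 6.67 | Both durations, e = 6.67 | Both durations, e = 0 |
|---|---|---|---|---|---|
| 4–16 | 44 | 5.4; 80% | 6.9; 58% | 11.8; 25% | 24.2; 9% |
| 0–16 | 44 | 5.1; 83% | 6.1; 69% | 10.8; 28% | 23.7; 9% |
| 4–16 | 100 | 3.6; 99% | 4.8; 88% | 8.1; 46% | 16.2; 15% |
| 0–16 | 100 | 3.4; 99% | 4.2; 95% | 7.3; 54% | 15.8; 16% |

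**If the effect grows.** Take 5, 10 and 15 points at 4, 8 and 12 months, that is 1.25 points per month. The mean app effect is (6×5 + 4×10 + 2×15)/12 = 8.3. The uncentred arm term is exactly 0 and the interaction carries everything. The month-adjusted common effect is 3.1 (months 4–16) or 3.9 (months 0–16). On the odds scale, 30% to 45% is an odds ratio of 1.91. If the log odds ratio grew linearly from nil to that value at 6.67 months, the arm odds ratio would be 1.00, against 1.47, 2.17 and 3.20 at 4, 8 and 12 months.

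**The case against.** The strongest reply is that the plan never makes the uncentred arm coefficient its headline. It first states a comparison of all app wedges with all reference wedges, and it gives the interaction a separate purpose, effect modification. A fair reading is an overall odds ratio plus a secondary question. For the model as written, centring duration at its mean keeps about 99.7% power, so naming the contrast would be enough. And 44 is solved for, not stated. Section 3.2 lists 1,020 beds. With 72% on antimicrobials (the 2018 survey in the Introduction) and an assumed 50–100% occupancy, that averages 61 to 122 inpatients on antimicrobials per hospital before outpatients, though small hospitals have fewer.

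Much of this stands. A reader might infer that the reported odds ratio simply is the zero-month effect. That needs continuous, uncentred coding, which the plan does not state. A reader might also infer a collapse to 9% power. That needs survey-month effects, a paper-duration slope and zero-centring together, and the plan mentions no survey-month effects. Nor would a null arm term under growth be the only result, since the interaction would show the effect.

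What does not stand is that clarifying the coding is enough. The model without survey-month effects handles calendar time only through a linear duration slope. Once those effects are added, centring no longer helps while paper duration stays in. Averaging the fitted app effect over the 12 app hospital-surveys against paper in the same month gives SE 9.6 or 9.3 points at m = 44, about 34–37% power.

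**Conclusion.** The concern holds in a limited form. The plan describes one primary model, that model has no single term equal to the powered effect, and no contrast or coding is named to supply one. How much this costs depends on choices left open. As written and uncentred, power for the arm term is 53–74% at 44 prescriptions and 86–98% at 100. As written and centred at mean exposure, almost nothing is lost. With survey-month effects and a paper-duration slope, power at mean exposure is 25–28% at 44 and 46–54% at 100.

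These figures rest on a linear approximation to hospital-survey means, equal survey sizes, the stated ICC applied across all surveys of a hospital, normal tests with only six clusters, and a constant 15-point effect except in the growth example. The lack of a named primary odds ratio rests on none of them.

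**What to change.** In the Statistical analysis text and the synopsis:

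- Name the primary result as one common app-versus-paper odds ratio over all app surveys, from a model with survey-month and hospital effects and no interaction. Give a model-standardised difference in proportions beside it, so that it can be read against the 15-point target.
- Drop the paper-duration term.
- Put app exposure in a secondary model, with 4, 8 and 12 months as categories, and report its exposure-averaged effect next to the primary result.
- Reconcile the text that dates app wedges from month 4 with Figure 2, where the first app survey is at month 8, and align the endpoint's twelve-month wording with the chosen contrast.

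The cost is a wording change and one extra model. The real downside is attenuation. If the effect builds with exposure, the common estimate is too low (about 3–4 points against 8.3 in the example), so both results must be shown. The exposure-averaged effect is less precise: weighted by app hospital-surveys over months 0–16, it has about 66% power at 41 prescriptions, where the common effect has 81%, and 95% at 100.

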3.1 Study design

The study design will be an open cohort stepped wedge cluster randomized controlled trial (SW-CRT) in six central/provincial hospitals across Laos. SW-CRT is appropriate in the Lao context because it requires fewer sites than a parallel cluster trial, but has similar observational periods for reference and intervention phases. As the interventions will be delivered by one team travelling to each cluster in turn, implementing in stages will be more practical. In addition, all participating hospitals will have access to the novel interventions at the end of the study. Prescribers are allowed to move in and out of clusters during the trial.

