Most recommendations are for empiric treatment. For pathogens and syndromes for which Lao data are available, common causative pathogens and their antimicrobial susceptibilities are provided as a guide. This guideline also refers to some specific Lao treatment guidelines (e.g. Dengue guideline for diagnosis and treatment, Lao PDR or National Guidelines for the Use of Antiretroviral Therapy in Adults and Children) to avoid duplication.

Common and important infectious diseases are arranged by involved organ systems. Each infectious disease section includes causative pathogen (s) of the diseases, choices of antimicrobial regimen (primary and alternative), doses, duration and important notes on allergy or toxicity or to help guide treatment.

b. Reference phase

Study duration will be divided into two parts, reference and intervention phases. At the start (month 0), a point prevalence survey (PPS) on hospital antimicrobial use will be performed (more details on conduct of PPS are given in following section) to collect baseline data before introducing paper-based guidelines. The participating hospitals will receive a report of the PPS findings within one month of the survey (Appendix A4).

After PPS, all medical doctors of each participating hospital will be asked to complete an AMS knowledge survey (Appendix A5) and pre-prescribing guidelines survey (Appendix A9). Then, paper-based prescribing guidelines in both adult and paediatric versions (one adult guideline and one paediatric guideline) will be distributed to all doctors at participating hospitals, followed by guideline introductory session of the guidelines (Appendix A6). This session will not cover how to diagnose infectious diseases or prescribe antimicrobials but how to use these guidelines.

After introduction of the paper-based guidelines, all six hospitals will be formally included in the reference period. PI and research team will not become involved with any antimicrobial prescribing decisions of local prescribers at participating hospitals for individual patients. There will be contact details of the PI in the guidelines in case any prescribers need more clarification on the guidelines. A prescriber feedback survey on the paper-based version will be performed just before each paired hospital enters to the intervention phase (month 4, month 8 and month 12 after introduction of the paper-based prescribing guidelines).

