Date, time and venue: the session will take a maximum of 30 minutes with 10 minutes of discussion/questions. Session date, time and venue will be informed to all doctors one week in advance and again 3 days before starting the session. The session will be run in each hospital separately after conducting point prevalence survey (PPS) of hospital antimicrobial use and after all doctors have completed survey form on AMS knowledge for baseline data. Verbal consent will be asked from participants to record participant's names, age, sex, working positions, departments, years of work and phone number onto the session registration sheet.

Instructor: The principal investigator of the study will be the session instructor. Training will be given in the format of a PowerPoint presentation, following by question and discussion.

Session material: paper versions of both adult and paediatric prescribing guidelines will be distributed to doctors who participate to this session. A handout of the introductory session (the same standard session for all hospitals) will also be provided.

Session details include introduction of the guidelines, objectives of guidelines, guidelines skeleton and how to use these guidelines, see details as below:

1. Introduction to the guidelines

This guideline is based on:

- existing Lao treatment guidelines
- current data on infectious disease pathogens and antimicrobial susceptibility patterns in Laos
- international antimicrobial prescribing/treatment guidelines (e.g. WHO, CDC, NICE, IDSA, Sanford)

- both Lao and international clinicians, international infectious diseases experts and microbiologists contributed to this guideline

2. Giving the purpose of the having these guidelines:

- To support therapeutic clinical decision-making of Lao clinicians
- To guide the reasonable use of antimicrobials to optimize cure and control antimicrobial resistance in Laos
- To promote the use of essential medicines registered with the Lao Food and Drug Department
- To diminish the cost of care for infectious diseases whilst ensuring optimal treatment
- To promote patient safety by diminishing risks of allergy or toxicity
- To promote the use of microbiology laboratory techniques for infectious disease diagnoses and for guiding treatment

3. Explanation of overall guideline skeleton

- Therapeutic section
- Prophylactic section
- AMS section
- References
- Contact details

4. How to use these guidelines

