Daily Nearly every day Weekly Monthly Never

5. How often do you access this provided paper-based prescribing guidelines?

Daily Nearly every day Weekly Monthly Never

6. How often do you access other prescribing guidelines?

- Daily Nearly every day Weekly Monthly Never

7. How would you rate these paper-based prescribing guidelines overall?

- Very good and fitting with Lao context Good but need a bit more editing
 Moderate and need more editing Not good and need to review many sections

Please give comments in the box below:

A11. Prescriber feedback survey on mobile phone app prescribing guidelines

Prescriber feedback survey on mobile phone app prescribing guidelines

Date: ___/___/____, Year of graduation from medical school: _____, Speciality: _____,
Department: _____ Hospital: _____

1. Have you ever seen this antimicrobial prescribing guideline mobile phone application?

Yes No ; If answer is “No”, you do not have to continue this survey

2. If yes, have you ever used it?

Yes No ; If answer is “No”, you do not have to continue this survey

If the answer is “Yes”, please continue the survey

3. Complete this table below: Instruction: please indicate your level of agreement with the statement listed below (by ticking the box):

	Strongly agree	Agree	Neutral	Disagree	Strongly disagree	No opinion
The structure and design are easy to follow						
I can find information which I look for more easily than from paper-based guidelines						
Language font size and colour are easy to read						
Prescribing instructions (antibiotic of choice, dose and duration) are easy to follow						
Links to extra information (data on antibiotic susceptibility pattern, causes of infections in Laos, international recommendation) are useful						
The offline mode makes it easy for me to access the guidelines anywhere						
The App guideline encourages me to document the indication for antimicrobial on hospital charts						
The App guideline encourages me to document the duration of antimicrobial on hospital charts						
The App guideline has increased my knowledge of antimicrobial stewardship (AMS)						
Antimicrobial stewardship training increased my knowledge of AMS						

4. How often do you prescribe antimicrobial (s)?

Daily Nearly every day Weekly Monthly Never

5. How often do you access paper-based prescribing guidelines?

Daily Nearly every day Weekly Monthly Never

6. Do you carry your smart phone (with this prescribing guideline App) with you at work?

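### Scoring no opinion as 0, below strong disagreement, lets a gap in the share of zeros move the Mann-Whitney satisfaction result (secondary endpoint 4)

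*Combined protocol and SAP*

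**What the plan says.** Section 3.6 defines secondary endpoint 4 as prescriber satisfaction with, or acceptability of, the guidelines, app versus paper, at four months of exposure in each group.

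The Statistical analysis text scores answers from 5 (strongly agree) down to "strongly disagree=1, no opinion/not use=0". It continues: "Mann-Whitney test will be used to assess the differences between paper-based population and mobile phone app population". No sentence removes, recodes or separately reports the zeros, and no item or total score is named as the endpoint.

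The forms (Appendices A10 and A11) work differently. Questions 1 and 2 ask whether the respondent has ever seen and ever used the format. Anyone answering no is told "you do not have to continue this survey", which comes before the Likert table. The table's last column is for no opinion only; there is no box for non-use.

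On access, section 3.5 b says paper guidelines "will be distributed to all doctors at participating hospitals", while Appendix A6 says "paper versions of both adult and paediatric prescribing guidelines will be distributed to doctors who participate to this session". Section 3.1 adds: "Prescribers are allowed to move in and out of clusters during the trial". For the app, section 3.5 c.1 says the project will "not provide a smart phone to any physician without one (approximately <10% of physicians in provincial hospitals".

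On timing, the paper survey takes place just before each pair crosses over, at "month 4, month 8 and month 12 after introduction of the paper-based prescribing guidelines". Note a in section 3.5 c.3 and the app-survey paragraph of section 3.7 put the app survey at month 16. The second footnote to Figure 2 puts it four months after each launch.

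**The concern.** A rank test treats 0 as the worst opinion on the scale, but no opinion is the absence of one. If more respondents tick it in one survey than in the other, the test registers lower satisfaction even when everyone with a view thinks the same of both formats. The same mechanism can hide a real difference.

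The label also bundles two things. No opinion is a ticked box; non-use is recorded in questions 1 and 2 and leaves the table blank. The plan does not say whether a blank table becomes 0 or missing, so two analysts could get different results from the same forms.

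At stake is the app-versus-paper acceptability result. The primary endpoint does not use this scale.

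**Working it through.** The plan states no sample size, power or effect for satisfaction, so there is no figure to reproduce.

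**Inputs from the documents.** Codes 0 to 5, Mann-Whitney test, 5% level (two-sided assumed). Physicians in section 3.2: 222 + 30 + 66 + 18 + 60 + 30 = 426, an upper bound per survey.

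**Assumed inputs.** Zero shares; the distribution of scores 1 to 5; 200 respondents as a smaller case; one positively worded item; independent respondents; no hospital clustering.

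**Exact shift.** Let zp and za be the zero shares on paper and app, with scores 1 to 5 identically distributed. Then

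P(app > paper) + ½P(tie) = (1 − za)zp + ½·za·zp + ½(1 − za)(1 − zp) = ½ − (za − zp)/2.

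At 5% v 10%: 0.045 + 0.0025 + 0.4275 = 0.475. The shape of scores 1 to 5 does not matter.

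**False rejection** (4,000 simulated tie-corrected tests per scenario; scores 1 to 5 at 5/10/20/40/25%, 2/5/15/50/28% and 10/20/40/20/10%):

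| Scenario | 200 per survey | 426 per survey |
|---|---|---|
| Zeros 5% v 10% | 14.7–15.0% | 25.5–26.4% |
| Same, first distribution, same doctors in both surveys (assumed latent correlation 0.5) | 10.7% | 21.6% |

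Equal shares (5 v 5, 10 v 10) gave 4.2–5.8%, and zeros dropped when unrelated to opinion gave 4.3–5.9%. A further simulation of 5% v 10% gave 14.6% and 24.8%. For 10-point gaps of 0 v 10, 5 v 15 or 10 v 20, rejection was 24–27% at 100 per survey and 74–77% at 426.

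**Masking.** The true app advantage cancelled at 5% v 10% is [0.5 − zp(1 − za) − zp·za/2] / [(1 − zp)(1 − za)] = (0.5 − 0.045 − 0.0025)/0.855 = 0.529.

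**Is exclusion neutral?** Only if zeros are unrelated to opinion. Below, underlying opinions are identical (first distribution), paper zeros are 5% at random, and app zeros are likelier among doctors who would score 1 or 2. The true value is 0.500. Rejection is at 200 / 426 per survey.

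| App zero chance, scores 1–2 v others | Ranked: estimate; rejection | Excluded: estimate; rejection |
|---|---|---|
| 20% v 8.2% (10% overall) | 0.482; 11.3 / 15.0% | 0.508; 6.2 / 7.1% |
| 30% v 6.5% (10% overall) | 0.489; 7.0 / 8.7% | 0.517; 8.7 / 13.8% |
| 40% v 4.7% (10% overall) | 0.496; 5.0 / 5.0% | 0.525; 15.0 / 25.4% |
| 60% v 7.1% (15% overall) | 0.482; 10.4 / 15.3% | 0.540; 27.9 / 52.2% |

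The two analyses fall on opposite sides of 0.500 in every row, so each shows what the other misses.

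**Negatively worded items.** A10 has three: restricted choice, too much detail, and bulk. Agreement there is unfavourable, so a 0 falls on the favourable side.

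**Exposure at survey, paper v app months:**

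| Pair | App survey at month 16 | App survey four months after launch |
|---|---|---|
| First | 4 v 12 | 4 v 4 |
| Second | 8 v 8 | 8 v 4 |
| Third | 12 v 4 | 12 v 4 |

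Either schedule gives equal exposure in one pair of three.

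**The case against.** The forms already filter out most non-use. A respondent who follows the skip instruction gives no Likert scores, so the zeros certain to arise are no-opinion ticks by users, and the documents give no reason to expect those to differ between formats. This stands: it makes the ticked column the definite defect and leaves the coding of blank tables as an open question.

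A reader might infer that the coding is bound to penalise the app, because doctors without a phone would score 0. The documents do not support that. It requires skipped tables to be coded 0, which is nowhere stated. The phone figure covers provincial hospitals only: under 10% of 204 physicians (426 − 222) is at most 20, or 20/426 = 4.7 points, with nothing known about Mahosot's 222. Paper non-use could offset it, since A6 ties paper copies to attendance at the month-0 session and prescribers may arrive later.

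A reader might also infer that dropping the zeros is the unbiased answer. In three of the four opinion-linked scenarios above, at both sample sizes, the planned ranking rejects less often than exclusion. For an endpoint that includes acceptability, placing non-use lowest is a defensible composite; it is much less so for a user with no view. This part of the objection shapes the remedy.

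On timing, section 3.7 deliberately seeks paper opinions at several time points. But the same paragraph speaks of equal paper and app exposure, so the conflict remains.

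**Conclusion.** The scoring is wrong as written, for secondary endpoint 4 only. It places no opinion below the worst opinion in a rank test, and a gap in zero shares moves the estimate by half that gap. At an assumed 5% v 10%, with identical opinions, that means 0.475 instead of 0.500 and false rejection of about 15% (200 per survey) or 25% (426).

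The mechanism is certain if zeros enter the test. That is the natural reading of a six-category scale followed directly by the test, although the plan does not say so outright. The size is conditional on shares the documents do not give, and the direction is unknown. The simulated rates also rest on independence within and between surveys; if the same doctors answer both, the assumed correlation lowers them.

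The conflict over survey timing is a separate point and adds nothing to the size of this one.

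**What to change.** In the Statistical analysis text:

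1. Take no opinion off the ordered scale and run the rank comparison on scores 1 to 5.
2. State that skipped tables are not scored 0 in that comparison.
3. Report by survey the percentages never seen, never used (questions 1 and 2 of A10 and A11) and with no opinion.
4. Beside it, with equal prominence, give an acceptability analysis that ranks non-use lowest.

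Restricting the comparison to the statements A10 and A11 share (structure, prescribing instructions, extra information, documenting indication, documenting duration, AMS knowledge) is optional; some pairs match only loosely in wording.

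Separately, reconcile note a and the section 3.7 app-survey paragraph with the Figure 2 footnote and with the endpoint's four months in each group, and state paper exposure as 4, 8 or 12 months.

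The cost is analysis and endpoint wording only; the forms already collect what is needed. The downside is that the 1-to-5 comparison describes only users with an opinion, so it must be read with the non-use percentages and the acceptability analysis.
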